### *Secondary Aim:*

4. To develop and test cost-efficient and rapid measures to assess levels of exposure from oral tobacco products (determining exposure based on used oral tobacco products) and cigarettes (examining solanesol levels from cigarette filters).

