### **Hypotheses**

#### *Primary Aims:*

1. Instructions for use will lead to significant differences in patterns of use, which will be related to biomarkers of exposure.
2. Time in study will have an effect on outcome measures and will reach a plateau by at least 6 weeks.
3. Moderators for exposure will include pattern and intensity of tobacco product use. Pattern and intensity of product use will be affected by subjective responses to products,

perception of safety of the product, gender, race, age, degree of dependence and nicotine metabolism phenotype.

*Secondary Aim:*

4. Biomarkers of exposure will be related to levels of chemical constituents extracted from used oral tobacco pouch products in the complete substitution condition, plus levels of solanesol in filters in the partial substitution condition.

The outcome of this study will provide guidance on methods and measures that should be used in clinical trial assessments of tobacco products (e.g, MRTPs or new tobacco products). Furthermore, this study will novelly consider the interactions and effects of instructions of product use, perception and response to the product, and individual differences on product uptake and use and toxicant exposure.

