Because we are proposing to use an oral tobacco product, we will also be examining and testing measures of exposure. For example, for oral tobacco products, determining the effects of oral tobacco topography and its relation to exposure biomarkers has been limited to a few studies (27, 28). Novel methods, such as determining the amount of tobacco constituents extracted after use and relating these findings to biomarkers of exposure of these constituents, have never been explored, yet may prove to be cost-efficient compared to biomarker assessments. Similarly, measuring the solanesol levels, a tobacco-specific compound in cigarette filters, as an indicator of exposure has shown promise and may be another cost-efficient, rapid and simple measure of exposure, but requires further validation studies (29-31).

*Conceptual framework for tobacco product evaluation.* Clinical trials are a critical component of tobacco product evaluation (5, 32). Figure 1 shows a framework for the evaluation of tobacco products.

Figure 1. Conceptual Framework for Tobacco Product Evaluation

The primary goals of pre-clinical non-human and pre-market human product evaluation studies are to determine the

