#### **Product constituent testing:**

Pouches of used smokeless tobacco product will be obtained for chemical constituent analysis. Prior to the clinic visit at week 4 subjects will be asked to collect all used samples during the 24 hours before the visit. These samples will be placed in a small cooler and brought to the clinic visit. In addition, five unused oral tobacco pouches from their tin will be collected. Both these samples will be frozen. These samples will be shipped on dry ice to the CDC when samples from all the visits have been collected. At the CDC, the levels of selected chemical constituents in the unused and used pouch will be analyzed. These chemical constituents include nicotine, tobacco specific nitrosamine (NNK, NNN), BaP and catechols. Solanesol in cigarette filters will also be tested by CDC, which is a measure of tobacco smoke exposure (see 30, 31 for description of analysis conducted at CDC).

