**Hypothesis 1** will be analyzed by fitting a linear mixed model for each of the outcome measures (using week 6 as the primary endpoint): total NNAL, NNN, phenanthrene tetarol, mercapturic acids, PGEM, 8-epi-PGF2α, Total nicotine equivalents; and cardiovascular risk factors.. The mean model will include an effect for time, group and a time by group interaction. Specific hypotheses will be tested by testing the significance of the appropriate contrast. A secondary analysis will be completed adjusting for important factors such as environmental toxicant exposures, nutrition, stress and health to determine the effect their inclusion has on the association between group and the outcomes. Finally, we will complete an exploratory analysis that includes a site by group interaction to determine if the group effect changes by location.

**Hypothesis 2** will be analyzed by fitting separate linear mixed models for each group using biomarkers, snus topography, cigarettes and other subjective responses as the outcome. We will test for significant time effects and present plots of the outcomes to visually represent the time effects. Stabilization will be considered to have occurred when the variance between time-points does not exceed the coefficient of variation of the measures as assessed in the usual brand smoking group.

**Hypothesis 3** will be analyzed using a linear mixed effects models with a mean model that includes time, group and potential moderators (e.g., use patterns, age, sex, dependence, subjective responses, etc.). Interactions between group and the potential moderators will be included in the model and tested to determine if the potential moderator modifies the effect of group on the outcome (total nicotine equivalents, total NNAL).

**Hypothesis 4** will be evaluated using scatter plots and other visual methods. Associations will be summarized by Pearson's or Spearman's correlation coefficient, as appropriate, and formal inference will be completed using linear regression.

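### Hypothesis 4 tests for a non-zero association without pouch or cigarette counts or a performance criterion, so significance would not show that the assay improves on a count

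*Combined protocol and SAP*

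**What the plan says.** The secondary aim in section 2.0 is "To develop and test cost-efficient and rapid measures to assess levels of exposure from oral tobacco products", and likewise from cigarette filters through solanesol. Hypothesis 4 has two parts. The pouch part reads "Biomarkers of exposure will be related to levels of chemical constituents extracted from used oral tobacco pouch products in the complete substitution condition". The filter part continues "plus levels of solanesol in filters in the partial substitution condition".

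Section 7.0 gives the whole analysis in two sentences. Apart from scatter plots and other visual displays, "Associations will be summarized by Pearson's or Spearman's correlation coefficient, as appropriate", and then "formal inference will be completed using linear regression". It names no covariates, no target for correlation, R-squared or prediction error, and no comparator. The sample-size paragraph concerns NNAL under Hypothesis 1, so Hypothesis 4 has no stated n or power.

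On collection, section 6.4 (Product constituent testing) says: "Prior to the clinic visit at week 4 subjects will be asked to collect all used samples during the 24 hours before the visit". It adds that "the levels of selected chemical constituents in the unused and used pouch will be analyzed". The clinic-visit procedures in the same section refer to the amount extracted over the 24-hour collection. Neither place says whether the analysis variable is a value per pouch or a 24-hour total.

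**The concern.** A 24-hour total is the number of pouches multiplied by the extraction per pouch. The biomarker also rises with the number of pouches. The two can therefore be correlated even if the chemistry says nothing about how much a person absorbs from a pouch. Solanesol summed over a day's filters stands in the same relation to the number of cigarettes smoked.

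The aim is to test a new measure meant to be cheap and quick. Counting pouches or butts is cheaper still and needs no frozen shipment or laboratory. A non-zero slope cannot separate an assay that adds information from one that repeats the count. A reader choosing measurement methods for later product trials would want to know which it is, and the planned analysis cannot say.

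**Working it through.** **1. Sample available.** There is no Hypothesis 4 figure in the plan to reproduce. The stated size is 138 per group, and 5 x 138 = 690 agrees with the total. The two complete-substitution arms hold 2 x 138 = 276. The sample-size paragraph assumes 40-50% abstinence, giving 0.40 x 276 = 110 to 0.50 x 276 = 138 abstinent subjects before drop-out. I use n=100 as a round figure for that group after some loss.

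**2. Model with uninformative extraction.** For each subject, with independent noise terms:
- x = log(count) + e, with SD(e) = 0.3 (log of the 24-hour extracted total)
- y = log(count) + u, with SD(u) = 0.5 to 0.8 (log biomarker)
- count: rounded gamma, mean 8 per day, CV 0.2 to 0.5

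The documents give none of these spreads; all are assumptions. A mean of 8 is in line with the usage figures in section 8.2.

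**3. Expected correlation.** With v = variance of log(count), r = v / sqrt[(v + 0.3²)(v + SD(u)²)]. Taking v ≈ ln(1 + CV²):

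| Count CV | v | r, SD(u)=0.5 | r, SD(u)=0.8 |
|---|---|---|---|
| 0.2 | 0.039 | 0.20 | 0.13 |
| 0.3 | 0.086 | 0.35 | 0.24 |
| 0.5 | 0.223 | 0.58 | 0.43 |

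The smallest r significant at two-sided 0.05 with n=100 is t / sqrt(n - 2 + t²) = 0.197, or about 4% of variance. Most cells exceed it, although e carries no information about u.

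**4. Simulated rejection of zero slope, n=100.**

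| Predictor | Count term in model | Count CV 0.2 | Count CV 0.3-0.5 |
|---|---|---|---|
| 24-hour total | No | roughly 27-60% | 74-100% |
| 24-hour total | Yes | about 5% | about 5% |
| Per-pouch value | No or yes | about 5% | about 5% |

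Ranges cover SD(u) from 0.5 to 0.8 and repeated simulation.

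**5. A second parametrisation.** Here the count-biomarker correlation is set directly at 0.3, with an extraction CV of 30%. At n=110, the 24-hour total is significant in 40% of trials at count CV 0.2 and 78% at CV 0.5. Adding the count brings both to about 5%.

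**6. Residual smoking.** Steps 2 to 5 let pouches alone drive the biomarker, which suits abstinent subjects. Suppose drop-out is 20%, so n is about 220 (0.8 x 276), and 55% are non-abstainers using 40% fewer pouches. If cigarettes contribute 4, 8 or 16 pouch-equivalents on average, significant positive results fall in 55-100%, 5-96% and 0-15% of trials. These inputs are also assumed. They show that figures for the full randomised sample cannot be relied on in either direction.

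**The case against.** The strongest reply is that the plan delivers what Hypothesis 4 states. It claims only a relation, and section 3.0 gives the benchmark as cost against biomarkers: the method has not been explored, "yet may prove to be cost-efficient compared to biomarker assessments". On that view a 24-hour total that follows the count is a legitimate exposure measure, and added value over a count is a further question. This stands, and it is why the planned correlation should stay.

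Four more points stand in part:
- Correlation coefficients and plots will be reported, so a weak association will be visible. Nothing says how strong it must be.
- Hypothesis 3 lists use patterns among the model terms for nicotine equivalents and NNAL, so use is modelled against biomarkers elsewhere, but not together with the assay.
- Section 7.0 does not rule out covariates in the Hypothesis 4 regression. It also names none.
- The aim is secondary and developmental, and no primary conclusion rests on it.

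A reader might infer that significance is almost guaranteed. The documents do not support that. It would need a 24-hour total, which they leave undefined, and a wide spread of counts. One of the two complete-substitution arms prescribes pouch numbers in two tiers, which tends to narrow the spread. A reader might also infer that the assay adds nothing to a count. That is not shown either: extraction may reflect time in the mouth, and the plan simply cannot tell.

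**Conclusion.** The point holds in a limited form. The formal inference for Hypothesis 4, read in the ordinary way as a test of zero slope, has no performance criterion and no use count. With a 24-hour total, a significant result could come from the count alone, so it would not show that the assay improves on counting pouches or butts. How often that would happen depends on spreads the documents do not give: the n=100 figures run from roughly 27% to 100%, and the problem disappears with a count term or a per-pouch measure. A per-pouch value would still need the count to predict daily exposure. The plan does not say that significance alone would validate the assay, so the risk lies in how the result is read. This is a cheap improvement to a secondary aim, with no consequence for the primary comparisons.

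**What to change.** In section 7.0, Hypothesis 4:

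1. State whether the extracted measure is per pouch or a 24-hour total.
2. Keep the planned correlation as the answer to whether the measures are related.
3. Add two nested regressions of each log biomarker. The first contains use only: pouch count and time in mouth for the pouch assay, or butt count for solanesol, with cigarettes smoked or abstinence status where relevant. The second adds the extracted constituent or solanesol.
4. Report the added-variable test, the gain in R-squared with a confidence interval, and the prediction error of both models.
5. Claim that the assay improves on a count only from this comparison.

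The inputs already exist: the daily IVR diary, the 24-hour pouch and butt collections, and the paper record of time in and out of the mouth. The cost is a paragraph of text and slightly more analysis. The downside is that a claim for the new measure becomes harder to make.

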#### Other Analyses of Interest

**Hypothesis:** Those subjects who rate the products positively on the Product Evaluation Scale, Drug Effects/Liking Questionnaire and Perceived Health Risks during the sampling phase and extent of willingness to pay for the product are more likely to use more products during sampling, remain in the study and use products during the clinical trial phase.

**Hypothesis:** Most subjects (controls) will choose the *ad libitum* partial substitution method for tobacco use the most and very few smokers will choose the complete substitution condition. The rate at which subjects choose the various methods for use will be summarized by the sample proportion and confidence intervals.

Interaction of components tested across all projects will be conducted under Core A

#### **Sample-size determination.**

A sample of size 138 per group (690 in the five groups) would be required to assure an 80% chance of demonstrating that complete substitution leads to higher reduction in NNAL levels compared to the partial substitution after controlling for baseline NNAL levels (assuming a correlation of 0.6 between baseline and follow-up NNAL scores, and an effect size of low to medium) and accounting for drop-out rates and an abstinence rate of 40 to 50%. See Human Subjects section for details.

**Randomization:** Stratified randomization will be generated by the Biostatistics and Informatics Core of this grant.

## **8.0 ADMINISTRATIVE CONSIDERATIONS**

### **8.1 Conduct of the Trial**

The study will be conducted in accordance with the International Conference on Harmonisation (ICH) for Good Clinical Practice (GCP), the Declaration of Helsinki, and the appropriate regulatory requirement(s).

The University Of Minnesota IRB will review all appropriate study documentation in order to safeguard the rights, safety and well-being of the patients. The study will only be conducted at sites where IRB/EC or Campus Administrator approval has been obtained. The protocol, informed consent, written information given to the patients, annual progress reports, and any revisions to these documents will be provided to the IRB by the investigator.

Essential clinical documents will be maintained to demonstrate the validity of the study and the integrity of the data collected. Master files should be established at the beginning of the study, maintained for the duration of the study and retained according to the appropriate regulations.

### **8.2 Data Management**

#### **Quality control and adherence to protocol procedures:**

Standard operating procedures will ensure that all study sites are following the same procedures. Face-to face training for research personnel will occur prior to the study, where the protocol and procedures will be carefully described. Case report books will be provided for the different sites to maximize parallel data recording. Each visit will have a checklist of all the measures that need to be taken and the order by which these measures are administered. As another measure to ensure data collection integrity, an experienced study monitor will make a visit to clinical sites after they have enrolled their first several subjects to make sure that the protocol is being followed carefully and all the data are being collected properly. Another onsite visit will occur after the initiation of the study. Regular telephone conference calls will occur among the research coordinators to provide updates on study progress, trouble shoot problems and to make sure that all protocol procedures are followed. On a once a month basis, the investigators will participate in this conference call. During these conference calls, the number of subjects enrolled, the data collection process, the results from data monitoring and other issues of concern will be discussed.

Urine and blood biosamples and pre- and post-use smokeless tobacco (ST) collections will be given individualized bar codes for each subject (See Biomarker Labeling SOP). Each site will receive barcoded labels which have been packaged at the research coordinating site (University of Minnesota). Most of the subjective measures will be administered via Qualtrics, a secured website for the subject to enter the date in electronic forms. Forms will include programming features to ensure valid data (i.e., input masks, validation criteria, skipout logic) and will be exported to files that are de-identified of any personal health identifiers.

All other data not captured directly in Qualtrics at the other sites (e.g., pencil-and-paper forms) will be sent to the coordinating site (with photocopies of originals maintained at the other sites). A data monitor will be available at the research coordinating site and irregularities (e.g., wrong date on the forms, inconsistent data) or missing data will be flagged by the monitor and sent to the site for comment or correction to ensure the integrity of the data.

All de-identified biosamples will be sent to the University of Minnesota on a quarterly basis. Lists of subject number and biosamples sent will be recorded by each site and when the samples are received, the researcher at the coordinating site will note each subject number and biosample that was received. The samples-received list will be posted on a secure website so that each site can check it against their own lists.

#### **Data Identification:**

Human subject consent forms will indicate corresponding subject ID and will not be stored with the data. Paper and pencil subjective forms, and other Case Report Forms (CRF) will be identified with subject number and initials, and visit number and date will be entered onto appropriate forms. Data entered into the database will be de-identified, with only subject number as a link. Biomarker samples will be labeled with a scanner barcode indicating study site, subject number, visit number, specimen type (e.g., urine, serum, saliva) and intended assay or biobank samples.

All records will be confidential. All shared date will be de-identified. A Certificate of Confidentiality from NIH will be obtained to protect subject data from subpoena. A study monitor from the University of Minnesota will review each site's records to ensure all the study records are accurate and that all consents have been signed, thereby having access to names of individuals at different sites. However, no record of this identifying information will leave the premises. All data from the subjects at the different sites will be on a secure web-site or sent to the University of Minnesota, and all information will be de-identified. All biosamples sent to the University of Minnesota will also be de-identified.

#### **Randomization Procedures:**

Randomization will be stratified by location and number of cigarettes smoked per day ( $\leq$  18/day vs.  $>$  18/day, the expected median number of cigarettes smoked per day) to assure balance across treatment groups. Treatment groups will be checked for balance on other factors post randomization and any imbalances will be accounted for in our analysis as described in the statistical analysis section.

Subjects who have completed the Sampling Phase and are interested and eligible (use of  $\geq$  14 sachets and used most days) will be entered into the clinical trial and randomized to one of 5 arms. Subjects will be randomly assigned to the groups in an unblended fashion using a blocked random assignment list generated by the Biostatistics and Informatics Core. Each study site will receive a copy of the Randomization List for their study site. Subjects will be assigned sequentially to the product associated with the next open randomization number. This randomization number will be entered into the CRF.

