chosen because it is now nationally marketed, and based on our pilot study, has levels of nicotine similar to a 4 mg nicotine lozenge and appears to be palatable to smokers. Participants will complete a daily diary via IVR about the amount of snus, cigarette or any other nicotine-containing product use. -

After 1 week when subjects return to the clinic, we will assess: 1) number of cigarettes, snus sachets, and other nicotine products used during the past 7 days; 2) responses to the Product Evaluation Scale, Drug Effects/Liking Questionnaire and the Perception of Health Risks; 3) consumer perception measures that examine risks, benefits and feelings associated with the product; 4) willingness/unwillingness to participate in the experimental phase of the study; 6) interest in switching from cigarettes to the Camel Snus if it were not for the study; 7) impact on interest in quitting tobacco use; and 8) interest in paying for the product and the amount the subject is willing to pay for the product to replace cigarette smoking (measures from Project 2). Compensation for Sample Phase: Subjects will receive \$5 for transportation, \$5 for IVR completion, and \$40 for trying the study product for 1 week for a total \$50, whether they want to continue with the study or not.

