#### ***Clinical Trial Phase:***

At the end of the sampling phase, eligibility for the clinical trial phase will be determined. Eligible subjects will have used an average of at least 2 sachets of Camel Snus daily during the sampling phase or at least 7 snus sachets used over most days during the sampling period. Subjects must be willing to attend clinic visits weekly for 4 weeks and biweekly visits for 6 weeks and a follow-up visit at 12 weeks post study product use and agree to be called at 4 and 24 weeks post-study. Subjects who wish to continue in the study will undergo 2 weeks of baseline where they will resume smoking and then will be randomized to one of five experimental conditions.

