#### **Baseline smoking period:**

Subjects will be required to attend baseline clinic visits during Week -2 (visit 91) and -1 (visit 00) of the clinical trial phase, and they will record their cigarette or other tobacco intake on a daily basis using an interactive voice response system (IVR) (see Table 1).

First baseline visit: This baseline visit will assess tobacco use status to determine if smoking has returned to levels prior to sampling phase. Subjects will collect a first morning void urine sample and bring it in on the day of their clinic visit for study biomarkers.

24 hours prior to second baseline visit: Prior to the second baseline visit, subjects will collect all of their cigarette butts in a container provided for the entire day.

Second baseline visit: Subjects will collect a first morning void urine sample on the day of their clinic visit. The 24 hour cigarette butt collection and urine sample will be brought with them to their clinic visit. Blood samples will be drawn for study biomarkers. Buccal cells will be collected 20 minutes after the subject brushes their teeth using a cytobrush rubbed against the buccal mucosa as per previous studies (34). Oxygen saturation, CO, vitals and weight will be obtained. Subjective measures will include predictors for MRTPs use, factors that may influence the biomarker measures, and outcome measures (see Tables 1 and 2).

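### Each site holds its own blocked randomisation list in an open-label trial, and nothing stated stops the next arm being known before a subject is entered

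*Combined protocol and SAP*

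**What the plan says.** Section 8.2, Randomization Procedures, sets out the process. Assignment is "in an unblended fashion using a blocked random assignment list" (the first adjective is evidently meant to be unblinded), and the Biostatistics and Informatics Core generates the list. Then: "Each study site will receive a copy of the Randomization List for their study site". Then: "Subjects will be assigned sequentially to the product associated with the next open randomization number". The only record it names is the number itself: "This randomization number will be entered into the CRF".

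Section 6.3 and section 8.2 both stratify by site and by cigarettes per day, split at 18. The short Randomization paragraph at the end of section 7.0 adds only that the Core generates the stratified list.

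On timing, section 6.4 asks at the end of the sampling week about "willingness/unwillingness to participate in the experimental phase of the study". Next, "Subjects who wish to continue in the study will undergo 2 weeks of baseline", and randomisation follows that baseline period. Of the first baseline visit it says: "This baseline visit will assess tobacco use status to determine if smoking has returned to levels prior to sampling phase".

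**The concern.** Masking after assignment and concealment before it are different protections. A trial that tells smokers to stop or to carry on cannot be masked. It can still keep the next arm unknown until the subject is committed. As written, the plan puts the full sequence at the site and does not provide for that.

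The comparison at risk is the one that was powered. The sample-size paragraph of section 7.0 is built on complete against partial substitution, with NNAL as the outcome, and allows for only 40 to 50% abstinence. The result therefore depends heavily on which smokers stay off cigarettes. If someone who could see the next arm steered motivated subjects towards a no-smoking slot, or discouraged unlikely quitters from one, the arms would differ at entry in traits the trial does not measure.

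**Working it through.** **1. What follows from the text.** The list fixes the arm for each slot, slots are used in order, and the strata (site, and 18 or fewer against more than 18 cigarettes per day) are known before assignment. Given a subject's stratum, the holder of the list can read off the next arm.

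**2. Search for a safeguard.**

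| Section | What it covers | List custody or concealment |
|---|---|---|
| 6.3 Randomization | Strata, later balance checks | None |
| 7.0, Randomization | Who generates the list | None |
| 8.2, Quality control | Training, checklists, site visits, data flags | None |
| 8.2, Data Identification | De-identification, review of records and consents | None |
| 8.2, Randomization Procedures | List, site copy, sequence | None |
| 8.2, Biobank | Locked storage of subject identifiers | None |

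**3. Decisions still open close to randomisation.**
- *Return to usual smoking.* Checked at the first baseline visit, with no numeric criterion and no stated consequence.
- *Willingness.* First asked at the end of sampling. No section requires it to be confirmed and recorded before the arm is seen.
- *Stratum.* Neither section 6.3 nor 8.2 says which cigarettes-per-day measure applies. Screening history and the daily telephone diary are both available, so a subject on different sides of 18 by the two measures could be placed on either list.

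In addition, the substance-use exclusion specific to the clinical trial rests on a questionnaire that Table 1, as extracted, places at the first baseline visit. Eligibility is then not fully settled when sampling ends.

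**4. Size of the exposure.** The plan gives no figure for predictability. Its own totals agree: 5 × 138 = 690.
- Lists: 3 sites (Overview of Experimental Design) × 2 strata = 6, or 690 / 6 = 115 slots each if equal.
- List in hand, stratum known: the next arm is certain at every one of the 690 assignments.
- List withheld, nothing else known: a given arm has chance 1/5 = 20%, and complete substitution has chance (2 × 138)/690 = 276/690 = 40%.

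Block size matters even if the list is withheld, because past assignments are visible in an open trial. The documents give no block size, so the sizes below are assumptions. With 5 equal arms, *k* slots per arm and block length *n* = 5*k*, the expected share of slots whose arm is certain is 1/(*n* − *k* + 1):

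| Assumed block | Certain share | Of 690 | Best guess correct |
|---|---|---|---|
| 5 | 1/5 = 20% | 138 | 46% |
| 10 | 1/9 = 11% | 77 | 41% |
| 15 | 1/13 = 8% | 53 | 38% |

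These counts assume complete blocks. Lists of exactly 115 would end in an unfinished block for sizes 10 and 15, in which no slot is certain. The counts then become 6 × 11 × 10/9 = 73 and 6 × 7 × 15/13 = 48. All these figures measure foreseeability, not bias.

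**The case against.** The strongest reply is that harm requires the list to be visible to people who enrol or judge subjects, and the plan does not say that it is. Section 8.2 leaves uniform site conduct to standard operating procedures that were not supplied, and these could contain the safeguard. That limit stands. The finding concerns what the plan states.

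Second, discretion is narrower than it may look. Most entry criteria are measured or counted: CO, NicAlert, days of substance use, sachets used. Section 8.2 randomises only subjects who are interested and eligible. The return-to-smoking check comes a visit before the end of baseline and excludes nobody on the text, so it is the weakest of the three openings. The stratum question affects only subjects whose two measures straddle 18. These points reduce the likely impact. They do not supply a record made before the arm is seen: being interested and eligible is a precondition, not a locked entry.

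Third, a list shows the arm for each slot, not which person will take it. Foreseeability for an individual arises only close to randomisation, which is when the remaining decisions are made.

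Fourth, the site count is not entirely secure. Section 8.3 mentions three other sites after naming the University of Minnesota. Four sites would give 8 lists of about 86 (690 / 8). Neither the 690 nor the block shares would change.

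Finally, the plan does mitigate. It adjusts for imbalances, controls for baseline NNAL, analyses by intention to treat and monitors records. These deal with measured differences, departures after assignment and the accuracy of data. None restores concealment, and no section asks monitors to check that entry preceded knowledge of the arm.

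**Conclusion.** The concern holds. Followed as written, section 8.2 lets whoever holds the site's list know the next arm at each of the 690 planned assignments before entry is fixed. This is more than missing detail, because the plan affirmatively sends the list to the sites. Whether selection would occur, and in which direction, cannot be worked out from the documents. The conclusion rests on the sections supplied and would fall away if an existing procedure already withholds the list from enrolling staff until entry is recorded. It should be fixed, since concealment cannot be restored after subjects have been randomised.

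**What to change.** In section 8.2, Randomization Procedures, replace the sentence that sends the list to the sites with text such as:

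> The Biostatistics and Informatics Core keeps the list and releases one assignment at a time, only after the site has recorded eligibility, willingness to continue and stratum. Block sizes are not disclosed to sites.

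If central release is not feasible, use sequentially numbered, opaque, sealed envelopes by stratum, held by someone with no part in screening, consent or eligibility decisions. State which cigarettes-per-day measure, over what window, sets the stratum. If a site procedure already provides concealment, say so in this section.

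Eligibility can be recorded cleanly only if the documents agree on it. The sachet criterion in section 8.2 and the one in section 6.4, Clinical Trial Phase, differ and must be reconciled.

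The documents give no costing. In our judgement the change is a small set-up task for the Core, which already generates the list, and a short delay at each randomisation. It needs no extra subjects, visits or samples.
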